3.3. Scheduled clinical visits

The assessment schedule (Table 1) lists all the assessments and when they are to be performed. Subjects will meet with study staff. When the visit doesn't include blood collection or BIA the visit can be made remotely. During the clinical visits, staff will review calendars, assess for signs and symptoms of adverse events, review compliance to the study product and answer any questions from the subject. Eligible participants will receive 3 different visits (Baseline visit (t0), and two follow-up visits (after 6 and 12 months from the baseline). Eligible participants will be telephonically contacted at the end of each FMD cycle (day 6) in order to assess signs and symptoms of adverse events, compliance to the nutritional intervention (see Appendix A, B), to answer to the questionnaire for dietary recall (see Appendix C).

4. Table 1 reports the timeline of the clinical visits and the activities scheduled. All data obtained from these assessments must be supported in the participant's source documentation.

	Screening Visit	Baseline visit (T ₀)	Follow-up visit 1 (T ₁)	Follow-up visit 2(T ₂)
Informed Consent	✓			
Review Eligibility Criteria	✓			
Start of intervention				
Physical examination ¹		✓	✓	✓
Vital Signs ²	✓	✓	✓	✓
BIA		✓	✓	✓
Peripheral Blood for genetic analysis		✓		✓
Hematological analyses ³		✓		✓
Pregnancy test	✓	✓		✓
AE and SAE collection		✓	✓	✓
Primary and secondary endpoints assessment		✓	✓	✓
Medications	✓	✓		✓

¹ height, weight (dress weight), waist and hip circumferences. ² Body temperature, blood pressure, pulse, respiratory rate. ³ Lipid profile (total cholesterol, LDL-cholesterol, HDL-cholesterol and triglycerides, serum/plasma, albumin, alkaline phosphatase, insulin-like growth factor 1 (IGF-1), Insulin-like growth factor-binding protein 1 (IGFBP1), creatinine, insulin, C-reactive protein (CRP),

aspartate aminotransferase (AST), alanine aminotransferase (ALT), homocysteine, glucose, glycosylated hemoglobin (HbA1c).

Screening and Baseline visit

Potential participants already subjected to a 5-day fasting-mimicking diet (FMD) program either alone or in combination with the longevity diet previously enrolled in one of the two interventional arms and who completed the clinical study NCT05698654 less than three months before the enrolment period will be contacted *via* telephone to determine preliminary eligibility and interest. Once participants meet all inclusion/exclusion criteria, they will be offered by study staff the opportunity to learn more about the research opportunity before any procedure is performed. Participants meeting eligibility will be then invited to attend a baseline and two follow-up visits

Baseline visit will include measurement of height, weight, and vital signs (body temperature, blood pressure, pulse, respiratory rate), completion of medical history questionnaire, review of medical history and current medications, and collection of fasting blood (12 mL: 6 mL for serum, 6 mL for plasma). Blood testing will include: complete blood count (CBC), glycated hemoglobin (HbA1c), glucose, insulin, lipid profile (total cholesterol, LDL-cholesterol, HDL-cholesterol and triglycerides), AST (GOT), ALT (GTP), alkaline phosphatase, creatinine, reactive C protein (PCR), albumin, insulin, IGF-1, IGFBP1, homocysteine as well as a urine pregnancy test in females of child-bearing potential. Fasting is defined as 12 hours of refraining from consumption of food and beverages though unlimited consumption of water is allowed and encouraged. Participants will be given three boxes of FMD together with ketone test strips to self-monitor urinary ketone bodies during the FMD cycles. Detailed information on the FMD plans will be also given during the visit. Baseline visit will also include body composition assessment using Bioelectrical Impedance Analysis (BIA), measurement of height, weight, and vital signs, medical history, current medications and a collection of fasting blood for the genetic analysis (25 mL: 7.5 mL for serum, 7.5 mL for plasma, 10 mL for white blood cells). Note, the typical draw volume for blood donation in Italy is ~450 mL. Blood testing information will be also retried from the screening visit.

Follow-up visits

The follow-up visits will be carried out after three (follow-up visit 1) and five (follow-up visit 2) FMD cycles (6 and 12 months), in order to evaluate the progress of the trial.

Follow-up visit 1

During the first follow-up visit, the study staff will assess the signs and symptoms of adverse events and review compliance to the FMD program. The visit will also include body composition assessment using BIA, measurement of height, weight, and vital signs, medical history and current medications. Participants will receive the FMD boxes for the remaining two cycles together with the ketone test strips for self-monitoring of urinary ketone bodies during the FMD cycles.

Follow-up visit 2

During the second follow-up visit, the study staff will assess the signs and symptoms of adverse events and review compliance to the FMD program. This visit will also include body composition assessment using BIA, measurement of height, weight, and vital signs, medical history and current medications. In addition, a collection of fasting blood for haematological and for the genetic analyses will be performed.

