4.4. Subject Compensation

Subjects will not be compensated for participation in this trial.

5. Study Product:

Formulation, Packaging, Labelling, Preparation, Administration, and Dosage of Study Products

The subjects will be instructed to follow their usual diet plan, except for the 5 days when they will be eating the foods included in the FMD box. The FMD diet is made up of nut bars, dehydrated soups, tea, olives, kale crackers, electrolyte beverages, and a chocolate crisp bar.

- Nut bars: Almond, macadamia nuts, pecans, vegetable inulin fibre (chicory root fiber), honey, coconut flour, flaxseed, natural flavour, sea salt, rosemary extract.
- Almond and Kale crackers: almonds, sesame seeds, tapioca flour, chia seeds, golden flax seeds, sunflower seeds oil, kale, sea salt, coconut sugar, coconut vinegar, onion powder, chili pepper, cumin seeds, black pepper, antioxidant: extract rich in tocopherol, garlic, origan, acidifier: citric acid.

- Electrolyte beverages containing water, natural vegetable glycerine, natural flavour,
- Olives.
- Spearmint tea, spearmint lemon tea, hibiscus tea.
- There are 5 different soups, which contain various combinations of rice flour, rice starch, potato flakes, tomato concentrate, sweet red pepper, basil, onion, leek, extra virgin olive oil, parsley, peas, yeast extract, savoy cabbage, carrot, garlic, spinach, celery, turmeric, black and white beans, champignon mushroom powder: minestrone, mushroom, tomato, vegetable, black beans soup;
- Chocolate crisp bar: inulin, almond butter, brown rice, cocoa powder, almonds, chocolate chips (brown sugar, cocoa mass, cocoa butter), rolled oats, brown rice syrup, flaxseed oil, rice dextrin, grape juice, salt.

To evaluate the adherence to the FMD and its metabolic effects, patients will receive ketone test strips together with each FMD kit to self-monitor urinary ketone bodies.

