5.1.5. Assessment of Subject Compliance with Study Product

Compliance will be measured using both a subject calendar provided by the investigator and direct verification of consumption of the FMD. Subjects will not be asked to return FMD boxes.

6. Description of Specific Testing Modalities

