6.4. Body Impedance Analysis

The BIA technique is based on the fact that lean tissues have a high water and electrolyte content, and thus provide a good electrical pathway. Fat contains a lower percentage of body water, and thus is a poor conductor of the electrical signal. Utilizing a low energy, high frequency, electrical signal (50 kHz, 500 micro amp), a measurement of the baseline resistance and reactance to the flow of electrical current can be made. The measurement relates directly to the volume of the conductor, which is used to determine total body water, lean body mass, and finally, fat mass and percent body fat measurement on the Tanita® scale.

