8.7. Interim analysis

We will perform an interim analysis of the results obtained by participants enrolled who have completed the 6 months of treatment in order to determine the efficacy of the treatment to positively affect primary and/or secondary endpoints of the study. Statistical analysis will be performed as mentioned in section 8.6.1 and 8.6.2

9. Ethical Considerations

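### If cycle 1 starts near T0, T2 falls within days to a few weeks of FMD cycle 5, while T0 is tied to no cycle and no minimum FMD-to-measurement interval is set

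*Protocol*

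**What the plan says.** Section 3 plans a 5-day FMD every three months for one year. Section 3.3 places "two follow-up visits (after 6 and 12 months from the baseline". The Follow-up visits text adds the cycle count: "The follow-up visits will be carried out after three (follow-up visit 1) and five (follow-up visit 2) FMD cycles (6 and 12 months". Three boxes are handed out at T0 and the remaining two at T1, five in all. The row of Table 1 for the start of the intervention carries no mark, and no other text dates cycle 1.

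For T0, the inclusion criteria (3.1.1) and Recruitment (3.2) require completion of the previous study less than 6 months before this one starts. The Screening and Baseline visit text describes people "who completed the clinical study NCT05698654 less than three months before the enrolment period". Section 3.1.3 also prohibits taking part in an investigational study in the 30 days before the start.

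The only contact timed to a cycle is a telephone call: "Eligible participants will be telephonically contacted at the end of each FMD cycle (day 6". On compliance, 5.1.5 says: "Compliance will be measured using both a subject calendar provided by the investigator and direct verification of consumption of the FMD". The primary analysis (8.6.1) models the change in fat mass from baseline to the second follow-up visit. Section 8.7 plans "an interim analysis of the results obtained by participants enrolled who have completed the 6 months of treatment".

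**The concern.** The primary contrast is within one arm, T2 against T0, with no concurrent control. Anything that differs systematically between the two visits, apart from a year on the regimen, goes into the estimate. Distance from the most recent FMD cycle is such a difference: the schedule pulls T2 towards a cycle and leaves T0 free.

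The protocol gives reason to take this seriously. Section 5 expects a cycle to have metabolic effects: "To evaluate the adherence to the FMD and its metabolic effects, patients will receive ketone test strips together with each FMD kit". Section 6.4 says that BIA yields a measurement "which is used to determine total body water, lean body mass, and finally, fat mass", so fat mass is reached through body water. The protocol standardises other short-term influences (a 12-hour fast before blood; 6 hours without caffeine, alcohol or tobacco before blood pressure) but sets nothing for the intervention itself.

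At stake are the T2-versus-T0 fat-mass contrast, the blood contrasts at the same two visits, and the interim look, which uses T1 soon after cycle 3.

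**Working it through.** **Inputs.** Five cycles of 5 days (Section 3; 3 + 2 boxes, Section 3.3). Visits at 6 and 12 months from baseline, taken as days 183 and 365. Two quantities are assumptions, because the protocol does not give them in days: *s*, the days between cycle starts, and *d*, the days from T0 to the start of cycle 1.

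**Formula.** Last FMD day of cycle *k* = *d* + *s*(*k* − 1) + 4. Gap = nominal visit day − last FMD day. A negative gap means that the nominal day comes before the cycle ends, so the visit would have to move later to follow the cycle as the protocol requires.

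**The plan's own figure.** With calendar-month spacing and *d* = 0, cycles start at months 0, 3, 6, 9 and 12. Three cycles by the 6-month visit and five by the 12-month visit are reproduced only if each visit sits just after the cycle starting in that month. At exactly month 12, four cycles are complete.

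| *d* | *s* (days) | Last FMD day, cycle 3 | Gap to T1 | Last FMD day, cycle 5 | Gap to T2 |
|---|---|---|---|---|---|
| 0 | 84 (12 weeks) | 168 + 4 = 172 | 11 | 336 + 4 = 340 | 25 |
| 0 | 89 | 178 + 4 = 182 | 1 | 356 + 4 = 360 | 5 |
| 0 | 90 | 180 + 4 = 184 | −1 | 360 + 4 = 364 | 1 |
| 0 | 91 | 182 + 4 = 186 | −3 | 364 + 4 = 368 | −3 |
| 7 | 84 | 7 + 168 + 4 = 179 | 4 | 7 + 336 + 4 = 347 | 18 |

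With calendar months (*s* about 91.3, *d* = 0), cycle 5 ends about day 365.2 + 4 = 369. The earliest T2 after it is about day 370, some 5 days past day 365.

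**When day 365 can follow cycle 5 at all.** This needs *d* + 4*s* + 4 ≤ 364. In whole days, *s* ≤ 90 at *d* = 0 and *s* ≤ 88 at *d* = 7. A later start makes it worse: with *d* = 30 and calendar-month spacing, the last FMD day is about 30 + 365.2 + 4 = 399, or 34 days past day 365.

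**T0.** Completion of the previous trial may lie up to about 91 days back (three-month limit) or 183 days back (6-month limit). The last FMD day of that trial is no later than its completion, by an amount not given here, so neither figure caps the distance from that trial's last FMD day. If the 30-day rule in 3.1.3 applies to the previous trial, T0 at the start of this study would be at least about 30 days from it, against 25 days or fewer at T2 in the scenarios above.

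**The case against.** Four objections have force.

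- **The T2 timing is conditional.** Nothing dates cycle 1, and the unmarked table row may be an artefact of text extraction. This stands: the gaps are scenarios and not maxima. But a start near T0 is the reading that best fits three-month spacing, five cycles and a 12-month visit together.
- **The harm is not demonstrated.** The ketone strips are for use during a cycle and say nothing about carry-over, and the BIA text is a general description. This also stands. A reader might infer that T2 fat mass will look too low, or that maintenance will be overstated. The protocol does not support that: it gives no size, direction or persistence for a recent-cycle effect.
- **The stated primary endpoint is different.** It counts participants who keep at least half of the fat mass lost in the previous trial. The timing of that trial's visits relative to its cycles is not shown, so a mismatch with that reference cannot be judged. Measuring people while on the regimen is also a legitimate choice. The point is therefore confined to the T2-versus-T0 contrast that 8.6.1 specifies and to the interim look.
- **Some of this belongs in a SAP.** How an analysis uses the interval can sit there, and its absence here is not held against the protocol. When measurements are taken relative to a cycle is visit conduct, which a SAP cannot repair afterwards.

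The 3-month and 6-month limits are a separate eligibility matter. Both are upper limits counted from different dates, and their conflict does not create the asymmetry.

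**Conclusion.** The point holds in a limited form and should be addressed. As written, the schedule can place T2 from about one day to about 25 days after cycle 5, assuming that cycle 1 starts near T0 and that spacing lies between 12 weeks and calendar months. T0 has no link to the last FMD day of the previous trial, and the 30-day rule, read literally, would widen the difference. The primary contrast can then compare visits at systematically different distances from a cycle, with no concurrent control to absorb the effect. Whether this biases fat mass, by how much and in which direction cannot be determined from the protocol.

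A reader might also infer that the visit schedule is impossible. It is not: five cycles fit before day 365 if spacing is slightly shorter than three calendar months, and otherwise T2 need only fall a few days late when cycle 1 starts at T0.

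**What to change.** Leave the number and timing of cycles unchanged, and keep T2 after cycle 5.

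1. In the visit descriptions of Section 3.3, state a minimum interval, its length set by the sponsor, from the last FMD day to BIA, weight, blood pressure and blood at every visit where each is taken.
2. Add a visit window for T1 and T2, and align with it the 6- and 12-month wording in Section 3.3 and the one-year wording in 8.6.1.
3. Record days since the last FMD day at T0, T1 and T2. For T1 and T2 the calendars and day-6 calls can supply it; for T0 the previous trial's records would be needed. A supportive analysis of the primary contrast can then use it. Where the T0 and T2 intervals do not overlap, say that adjustment cannot separate interval from visit.
4. Separately, reconcile the 3-month and 6-month limits, the date each counts back from, and how the 30-day rule in 3.1.3 applies to the previous trial.

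The cost is some wording, one recorded number per visit and one supportive analysis. T1 and T2 may fall somewhat after the nominal month, and a few baseline visits may be delayed. A minimum interval does not make T0 and T2 equally distant from a cycle. It keeps measurements clear of the days right after one, and the recorded interval shows how much difference remains.

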2.2. Endpoints

- 2.2.1. *Primary endpoint*: maintenance of at least 50% of the fat mass lost during the previous trial and measured after one follow up year on FMD every 3 months
- 2.2.2. *Secondary endpoints*: maintenance of at least 50% of one or more risk factors improvements achieved during the previous clinical trial and measured after one year of follow up FMD cycles every 3 months including improvements in: body mass, body mass index, blood pressure, IGF-1, haemoglobin A1c, fasting glucose, LDL, total cholesterol, and C-Reactive Protein. Determine long-term trends in the reduction/stabilization in the use of antihypertensive and glucose-lowering drugs or other commonly used medications.

3. Study Design

Follow up clinical trial including participants of the approved studies “*Studio degli effetti della dieta mima-digiuno e della dieta della longevità sulla composizione corporea, fattori di rischio per malattie età-correlate e marcatori dell'invecchiamento in uno studio randomizzato*” and “*Studio degli effetti della dieta mima-digiuno e della dieta della longevità sulla composizione corporea, fattori di rischio per malattie età-correlate e marcatori dell'invecchiamento in uno studio randomizzato-2*” that will follow 5-day of the FMD meal program every three months, for one year.

Selection and withdrawal of subjects of the previous clinical study

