7.4.3. Modification of Study Product(s)/Intervention(s) for a Subject

No food substitutes are permitted. A reduction of food products, a hold of food or discontinuation of food product is allowed at the discretion of the study clinician.

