7.4.5. Stopping Rules for an Individual Subject

A study subject will be discontinued from further Study Product(s) administration for:

a significant reduction of BMI greater than 15% from baseline measurement and in any case of a BMI measurement lower than 22 Kg/m² for women and 23 Kg/m² for men during the follow-up visits; any clinical adverse event, laboratory abnormality, concurrent illness, other medical condition.

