7.4.6. Premature Withdrawal of a Subject

A subject may decide to withdraw informed consent for any reason. Premature discontinuation by a subject will be evaluated to assess the status of the subject at termination, and will be recorded in the subject's medical record and in the CRF.

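### The month-12 fat-mass visit is dated both by calendar and by number of FMD cycles, and the protocol does not say that participants who stop product are still measured

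*Protocol*

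**What the plan says.** Section 3.3 gives each eligible participant a baseline visit and "two follow-up visits (after 6 and 12 months from the baseline", with no condition on product taken. The Follow-up visits text after Table 1 says: "The follow-up visits will be carried out after three (follow-up visit 1) and five (follow-up visit 2) FMD cycles (6 and 12 months". Table 1 places BIA and endpoint assessment at the second follow-up visit (T2), and the text for that visit confirms it: "This visit will also include body composition assessment using BIA, measurement of height, weight, and vital signs, medical history and current medications". Section 8.6.1 analyses fat mass from baseline to that visit, which it dates at one year.

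Section 2.2.1 words the primary endpoint as maintenance of at least half of the earlier fat loss, "measured after one follow up year on FMD every 3 months".

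Four places deal with participants who do not take all the product:
- Section 7.4.3: "A reduction of food products, a hold of food or discontinuation of food product is allowed at the discretion of the study clinician".
- Section 7.4.5 opens its list of individual stopping criteria with: "A study subject will be discontinued from further Study Product(s) administration for". It does not mention later visits.
- Section 7.4.6, on withdrawal: "Premature discontinuation by a subject will be evaluated to assess the status of the subject at termination". No month-12 measurement is mentioned.
- Section 7.4.7, whose heading concerns a subject who discontinues study treatment, lets the principal investigator replace that subject.

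**The concern.** A site needs one rule for when T2 happens. If a cycle is held, the calendar rule and the cycle rule give different dates. If product is stopped, the calendar rule still calls the participant in at month 12, but the cycle rule never does. The protocol does not say which rule governs.

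This matters because the primary endpoint is a one-year maintenance status, and Section 8.6.4 plans to report the percentage reaching it. Stopping product can be related to that status: one criterion in Section 7.4.5 is a BMI fall of more than 15% from baseline, which would tend to remove people who have kept or extended their loss. Other reasons for stopping, such as an adverse event or intolerance, could remove people with a worse course. If a site followed the cycle rule, or treated stopping product as leaving the study and replaced the person, the month-12 measurement would not be taken. A statistical analysis plan can choose how to handle missing values, but it cannot supply a BIA reading that was never made.

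**Working it through.** **1. The plan's own figure.** Section 8.1 forecasts at most 267 participants. Taking 167 per intervention arm (Section 1.2) and the drop-out of 21% and 18% (Section 8.1): 167 × 0.79 = 131.93 and 167 × 0.82 = 136.94. Rounding each down gives 131 + 136 = 267, so the figure reproduces. It forecasts how many people can enter. It says nothing about how many will stop product afterwards.

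**2. Do the two visit rules agree on schedule?** Cycles every three months, with the first at month 0 (assumed, since product is handed out at baseline), fall at months 0, 3, 6, 9 and 12. That is three cycles by month 6 and five by month 12, so the rules agree for full, on-time adherence.

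**3. Where they part.**

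| Course | Calendar rule | Cycle rule |
|---|---|---|
| All five cycles on time | T1 month 6, T2 month 12 | T1 month 6, T2 month 12 |
| One three-month hold before the third cycle, cycle made up later | months 6 and 12 | about months 9 and 15 |
| One three-month hold after the third cycle, cycle made up later | months 6 and 12 | month 6 and about month 15 |
| Product stopped after the third cycle | months 6 and 12 | month 6; T2 never reached |

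The hold rows assume that a held cycle is postponed rather than dropped. The protocol does not say which.

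**4. What could follow for the rate.** Let d be the share who stop product, p the maintenance rate among those still on product, and q the rate among those who stopped. The rate in everyone enrolled is (1 − d)p + dq, so the on-product rate exceeds it by d(p − q). The sign depends on whether q is below or above p. The documents give none of d, p or q, so all values below are assumed.

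- With d between 10% and 30% and p between 50% and 70%, setting q = 0 lowers the rate by dp: from 0.10 × 0.50 = 5 points to 0.30 × 0.70 = 21 points.
- Over the same range, setting q = 1 raises it by d(1 − p): from 0.10 × 0.30 = 3 points to 0.30 × 0.50 = 15 points.
- Borrowing d = 18% or 21% purely as a scale gives 48 or 56 of 267 people. If p is 60%, the all-enrolled rate is 0.60 × 219/267 = 49.2% or 0.60 × 211/267 = 47.4% when every stopper fails. It is (131.4 + 48)/267 = 67.2% or (126.6 + 56)/267 = 68.4% when every stopper maintains.

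These are bounds under assumption, not estimates. People who drop out altogether miss T2 under either rule. Only those who stop product but would still attend are affected by the visit wording.

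**The case against.** The best reply is that the calendar reading already prevails. Section 3.3 is the scheduling section and sets no condition on cycles. The sentence that counts cycles also gives the months, and Section 8.6.1 dates the second follow-up visit at one year. On that view the cycle count is just the nominal equivalent of the calendar. Section 7.4.5 ends product administration, not follow-up, and withdrawal of consent has its own section. Staff review compliance at T2, so imperfect compliance is expected there. Section 8.1 says that all who meet the inclusion criteria are considered. The words on FMD in Section 2.2.1 can be read as naming the regimen, and the choice of analysis set may belong in a statistical analysis plan not shown.

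Much of this stands. A reader might infer that those who hold or stop product have no scheduled month-12 fat mass, and that the maintenance rate is therefore on-treatment only. The documents do not support that: the calendar visit is written down, and no section ends follow-up when product ends. Nor may the earlier study's drop-out be read as the number of month-12 values that the cycle wording would lose. Those who stop after month 6 would also have a BIA reading from the first follow-up visit.

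The reply does not remove the ambiguity. Section 8.1 says who is considered, not when a stopper is measured. Section 7.4.7 allows replacement on discontinuing treatment, which invites a site to treat stopping product as leaving the cohort. No text says the opposite.

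**Conclusion.** The point holds as an unresolved contradiction in visit timing, together with silence on whether participants who stop product are followed to month 12. The two rules diverge as soon as a cycle is held or product is stopped, and the protocol allows both. On the cycle reading, the primary result risks reflecting mainly those still taking FMD; on the calendar reading it need not. Which reading applies, how many people it would affect and which way the rate would move cannot be settled from the documents. The ranges above show only that a material shift in either direction is possible under plausible assumed inputs. The wording should be corrected because the remedy is simple and a missed measurement cannot be recovered later.

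**What to change.** - In Section 3.3 and the Follow-up visits text, anchor T1 and T2 to months 6 and 12 from T0, whatever number of cycles has been taken.
- In Sections 7.4.5 to 7.4.7, state that stopping product is not withdrawal from the study, that those who stop are asked to attend the remaining Table 1 visits including BIA, and that participants who are replaced stay in the analysed cohort.
- In Section 2.2.1, time the endpoint at month 12 from baseline and keep the result in those still on FMD as supportive.

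No stopping, holding or dosing rule changes. The visits and measurements are already in Table 1, so the change is mainly wording, plus the effort of bringing back people who have stopped product. The cost is that the stated maintenance rate may be less favourable, and some who stop will decline to attend, so missing values will be reduced rather than removed.
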